5.3.2 Reasons for Withdrawal

A study subject may be discontinued from participation in the study for the following reasons:

- Any clinical adverse event (AE)
- Withdrawn Consent
- Protocol Violation (e.g., violation of any exclusion criteria)
- Lost to Follow-Up

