5.3.3 Handling of Withdrawals

If a subject is withdrawn prior to the end the study, the reason for withdrawal will be documented and entered into the eCRF and if patient is willing to return to be assessed, the End of Treatment (Day 180) assessments will be completed. Documentation of withdrawal in the source documents should include a distinction between participant withdrawal from the study medication regimen and withdrawal from the study itself. In the former case case, the study medication is stopped, but the participant, if willing, continues with study visit assessments; in the latter, study medication and study visit assessments are discontinued.

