8.4 Methods and Timing for Assessing, Recording, and Analyzing Safety Parameters

8.4.1 Adverse Events

ICH E6 defines an AE as any untoward medical occurrence in a patient or clinical investigation subject administered a pharmaceutical product regardless of its causal relationship to the study treatment. An AE can therefore be any unfavorable and unintended sign (including an abnormal laboratory finding), symptom, or disease temporally associated with the use of medicinal (investigational) product. The occurrence of an AE may come to the attention of study personnel during study visits and interviews of a study recipient presenting for medical care, or upon review by a study monitor.

All AEs including local and systemic reactions not meeting the criteria for "serious adverse events" should be captured on the appropriate CRF. Information to be collected includes event description, time of onset, clinician's assessment of severity, relationship to study product (assessed only by those with the training and authority to make a diagnosis, which would include MD, PA, Nurse Practitioner, DO, or DDS), and time of resolution/stabilization of the event. All AEs occurring while on study must be documented appropriately regardless of relationship. All AEs will be followed to adequate resolution.

Any medical condition that is present at the time that the patient is screened should be considered as baseline and not reported as an AE. However, if it deteriorates at any time during the study, it should be recorded as an AE.

All AEs must be graded for severity and relationship to study product.

FDA defines an AE as any untoward medical occurrence associated with the use of a drug in humans, whether or not considered drug related.

Severity of Event: All AEs will be assessed by the clinician using a protocol defined grading system. For events not included in the protocol defined grading system, than the following guidelines will be used to quantify intensity.

- Mild: events require minimal or no treatment and do not interfere with the patient's daily activities.
- Moderate: events result in a low level of inconvenience or concern with the therapeutic measures. Moderate events may cause some interference with functioning.
- Severe: events interrupt a patient's usual daily activity and may require systemic drug therapy or other treatment. Severe events are usually incapacitating.

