10 STATISTICAL CONSIDERATIONS

10.1 Study Hypotheses and Statistical Analyses

For the primary outcomes of Stage I, t- and chi-square tests will be used to test whether the treatment group experiences superior PK at Day 14 and Tolerability at Day 42, respectively. If it is determined that the assumptions of the t-test are not met by the data, non-parametric statistical tests will be employed; Fisher's exact test will be used as deemed necessary. In the unusual occurrence that the study groups are not in equipoise with respect to the measured baseline demographic, behavioral and clinical characteristics, linear and logistic regression models will be used to compare the treatment groups, adjusted for any observed differences. The same aforementioned statistics techniques will be used for the secondary outcomes of Stage I as well as the primary and secondary outcomes of Stage II.

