10.3 Study Outcomes

Stage I- Randomized Open-Label, Parallel Group

Primary Endpoints

- 1. Pharmacokinetic superiority at Day 14
 - a) Inter- and intra- patient variability: Time to attain therapeutic plasma concentrations of itraconazole (> 500 mcg/L)
 - b) Interpatient variability as calculated by co-efficient of variation

Trough (pre-morning dose) sample will be collected at Days 14 and 42. Using validated LC-MS/MS methods, blood samples will be analyzed to quantify plasma concentrations of itraconazole and hydroxyitraconazole.

Participants should arrive to the trial site having **not** taken their morning dose of study drug.

Note: site investigators are discouraged from drawing independent PK laboratories to check itraconazole levels outside of the designated timepoints (Day 14)

2. Tolerability - ability to remain on study drug at Day 42 with less than a 7-day interruption of therapy

Secondary Endpoints

- PK at day 7 plasma concentrations of itraconazole- (comparative trough, steady state plasma itraconazole concentrations of SUBA-itraconazole 65mg capsules with food to itraconazole 100mg capsules with food over 7 days)
- 2. PK at day 42 plasma concentrations of itraconazole- (comparative trough, steady state plasma itraconazole concentrations of SUBA-itraconazole 65mg capsules with food to itraconazole 100mg capsules with food over 42 days)
- 3. Efficacy: clinical outcomes (time to relief of fungal signs and symptoms) at days 14, 28, and 42
- 4. Safety- defined as: adverse events that occurred in each study arm by Day 42
- 5. Tolerability ability to remain on study drug at Days 14 & 28
- 6. Days of Hospitalization and ICU stays at Day 42
- 7. Other health economic endpoints:
 - 1. Number of unscheduled procedures (i.e., labs, scans, etc.) at Day 42
 - 2. Total number of capsules taken at Day 42
 - 3. SF-20 (QOL) assessments at Day 42

Stage II- Open-Label, Extension

Primary Endpoint

- 1. Efficacy- Free from proven or probable invasive endemic fungal infection at Day 180
- 2. Tolerability- ability to stay on study drugs at Days 43 180.

Secondary Endpoints

- 1. Safety- Adverse events that occurred in each study arm between Days 43 180 or end of therapy
- 2. Days of Hospitalization (Days 1 180) defined as days of hospitalization and ICU stays from randomization to Day 180 or end of therapy)

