10.5 Safety Review

A comparison of adverse events reported per study arm will be quantified and compared.

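### The Stage II adverse-event endpoint starts at Day 43, so read alone it can flatter the arm with more early toxicity stops, and no adverse-event endpoint in Section 10.3 covers Days 1 to 180

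*Combined protocol and SAP*

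**What the plan says.** Section 3.2.2 and the Protocol Summary list the Stage II secondary outcome as safety by 180 and give no start day. Section 10.3 makes this Stage II secondary endpoint 1: "Adverse events that occurred in each study arm between Days 43" to 180, or end of therapy. Stage I has its own safety endpoint, "adverse events that occurred in each study arm by Day 42". The next Stage II endpoint counts "days of hospitalization and ICU stays from randomization to Day 180 or end of therapy".

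Section 10.5 adds one sentence: "A comparison of adverse events reported per study arm will be quantified and compared". It names no window, population or denominator. Section 10.1 says that the t-test, chi-square, Fisher and regression methods "will be used for the secondary outcomes of Stage I as well as the primary and secondary outcomes of Stage II".

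Section 5.3.2 lets a patient be discontinued for any clinical adverse event. Under Section 5.3.3, when only the drug is withdrawn, "the study medication is stopped, but the participant, if willing, continues with study visit assessments". Section 8.4.1 adds: "All AEs occurring while on study must be documented appropriately regardless of relationship".

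**The concern.** Having reached Day 43 on study drug is itself a result of treatment. It is close to the Stage I primary tolerability endpoint, so the trial allows that it may differ between arms. A table that starts at Day 43 leaves out the toxicity that drove patients off drug earlier. It also draws its later events mostly from patients who tolerated the drug.

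If one formulation loses more patients to early toxicity, its Stage II count can fall for that very reason. A reader who takes the Stage II table as the answer to safety by Day 180 could then rank the two formulations the wrong way round. The Section 10.1 methods do not guard against this, because the plan gives no Stage II safety denominator, no person-time and no rule for events after drug is stopped.

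**Working it through.** The plan gives no adverse-event or early-stopping rate, so it has no figure of its own to reproduce on this point. The check compares the windows and then uses assumed rates.

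**Windows side by side**

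| Item | Starts | Ends |
|---|---|---|
| Stage II safety outcome (3.2.2, Protocol Summary) | not stated | 180 |
| Stage I safety endpoint (10.3) | not stated; by Day 42 | Day 42 |
| Stage II safety endpoint (10.3) | Day 43 | Day 180 or end of therapy |
| Stage II hospitalization endpoint (10.3) | randomization | Day 180 or end of therapy |
| Adverse-event comparison (10.5) | not stated | not stated |

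**Who can contribute.** For a patient who stops drug before Day 43, end of therapy comes before the Stage II window opens. Read literally, that patient cannot contribute a Stage II event. For example, a patient who stops on Day 30, keeps attending and has an event on Day 60 would be in neither the Stage I nor the Stage II count, although Section 8.4.1 requires the event to be recorded.

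**Illustration 1: equal later risk.** Let e be the share of an arm stopped early for toxicity and q the later event risk in those who stay. Assume that early stoppers add no Stage II event, and count each early stop as one Stage I event.

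- Stage II rate per randomized patient = (1 − e) × q
- Rate from Day 1 = e + (1 − e) × q

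Take e = 10% in arm A and 30% in arm B, with q = 30%:

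- Stage II per randomized patient: 0.90 × 0.30 = 27% and 0.70 × 0.30 = 21%
- Stage II per patient entering Stage II: 30% and 30%
- From Day 1: 0.10 + 0.27 = 37% and 0.30 + 0.21 = 51%

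With 40 per arm (the allocation ratio is not stated; 1:1 is assumed), that is 10.8 and 8.4 patients in Stage II, against 14.8 and 20.4 from Day 1.

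**Range.** Arm B's Stage II rate per randomized patient is lower by q × (e_B − e_A). Its rate from Day 1 is higher by (1 − q) × (e_B − e_A). Take early stopping from 10%/20% to 5%/35% and q from 20% to 40%:

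- Stage II: lower by 0.20 × 0.10 = 2 points to 0.40 × 0.30 = 12 points
- From Day 1: higher by 0.60 × 0.10 = 6 points to 0.80 × 0.30 = 24 points

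**Illustration 2: event-prone patients leave first.** Assume that 30% of each arm is event-prone and that only these patients stop early.

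| Later risk, prone / other | Share of arm stopped early, A and B | Stage II rate per entrant, A and B | Rate from Day 1, A and B |
|---|---|---|---|
| 60% / 15% | 6% and 18% | 26.5% and 21.6% | 30.9% and 35.7% |
| 60% / 15% | 6% and 24% | 26.5% and 18.6% | 30.9% and 38.1% |
| 60% / 10% | 5% and 20% | 23.2% and 16.3% | 27.0% and 33.0% |

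First row, arm B: 0.12 of the arm is prone and still on drug. Later events are 0.12 × 0.60 + 0.70 × 0.15 = 0.177. Per entrant this is 0.177/0.82 = 21.6%, and from Day 1 it is 0.18 + 0.177 = 35.7%. Here the order reverses even with Stage II entrants as the denominator.

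**When the effect disappears.** If the later risks differ, arm B has the lower Stage II rate per randomized patient only while q_B/q_A is below (1 − e_A)/(1 − e_B). That limit is 0.90/0.80 = 1.13 for 10%/20%, 0.90/0.70 = 1.29 for 10%/30% and 0.95/0.65 = 1.46 for 5%/35%. If arm B's later risk is higher than that, the Stage II table ranks the arms correctly.

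The rates from Day 1 leave out Stage I events that did not lead to stopping. They therefore illustrate the mechanism and do not forecast the proposed endpoint.

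**The case against.** The strongest reply is that early toxicity is already reported. Stage I safety counts adverse events by Day 42. Staying on drug to Day 42 is a Stage I primary endpoint, and Days 14 and 28 are secondary. An arm that lost many more patients early would show it there. Section 10.5 can also be read as a whole-study comparison. All of this stands, and it limits the problem to the Stage II table read alone. It does not close the gap. A patient with events in both periods appears in both tables, so the two cannot be added to give the proportion with any event by Day 180. Section 10.5 does not say that it covers that period.

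A reader might infer that no endpoint in Section 10.3 spans the 180 days. That is not so: hospitalization and ICU days count from randomization, and inpatient hospitalization is a seriousness criterion (Section 8.4.2). The gap concerns adverse-event endpoints.

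The listed outcome may also be only a short label. No passage says that safety by 180 is cumulative, and tolerability by Day 180 is likewise defined over Days 43 to 180. The mismatch is thus an ambiguity to settle, though the Stage I safety and Stage II hospitalization endpoints favour a count from the start.

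Finally, the endpoint refers to each study arm and does not restrict itself to patients on drug, and willing patients stay in follow-up. If their events after stopping are counted, the selection is weaker. The end-of-therapy limit points the other way, and the plan does not settle the question.

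**Conclusion.** The point holds for the Stage II adverse-event table read alone. Its window depends on what happened in Stage I, and it can hide or reverse a difference in early toxicity. On the assumed rates, the arm with more early stops looks 2 to 12 points better per randomized patient in Stage II, while it is 6 to 24 points worse from Day 1. These figures assume equal later risk in both arms and no Stage II events from early stoppers. The documents give no rates from which to judge the actual size or direction.

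A reader might go further and conclude that early adverse events are lost, or that the trial's overall safety ranking will be wrong. The documents do not support either, because Stage I safety and tolerability report the early period. This is a secondary endpoint, and no primary result or sample size depends on it. It should still be corrected, because no adverse-event endpoint in Section 10.3 answers the Day 1 to 180 question.

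**What to change.** Redefine Stage II secondary endpoint 1 in Section 10.3 as adverse events from first dose to Day 180, by randomized arm, in all patients who took study drug. Report the number and proportion of patients with at least one event, and events per person-time. Include events recorded after drug was stopped, with the matching follow-up time in the denominator. Person-time is needed because follow-up after stopping depends on willingness, and the Protocol Summary allows therapy to end before Day 180.

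Give the Section 10.5 comparison the same window, population and denominator, and word the outcome in Section 3.2.2 and the Protocol Summary to match. Keep the Day 43 to 180 table as descriptive, labelled as conditional on having reached Day 43, so that late events remain visible.

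The cost is a change of wording and slightly more analysis. Appendix A already schedules adverse-event collection at every visit from Day 1 to Day 180, so no new data are needed. Events after stopping will be incomplete for patients who decline further visits, so the number lost in each arm should be shown beside the result.

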10.4 Data Review Committee

In addition to discrete laboratory parameters for PK, laboratory reports, days of hospitalization, ER and ICU stays, and safety reports; a data review committee (DRC) consisting of a DRC chair and 3 additional mycology experts will review data to determine safety and efficacy parameters as follows:

DRC-Assessments of Clinical Response (Baseline, Days 14, 28, 42, 84, 180)

| Outcome | DRC-Assessed Clinical Response |
|----------------|---|
| Success | Resolution of all attributable clinical symptoms, physical findings and radiography Partial resolution of attributable clinical symptoms, physical findings and/or radiography |
| Failure | No resolution and/or worsening of attributable clinical symptoms, physical findings, and/or radiography |
| Not applicable | No attributable signs and symptoms present at baseline and no symptoms attributable to IFD developed post-baseline |

DRC-Assessments of Mycological Response (Days Baseline, Days 14, 28, 42, 84, 180)

| Outcome | DRC-Assessed Mycological Response |
|----------------|---|
| Success | Eradication |
| | Presumed eradication |
| Failure | Persistence |
| | Presumed persistence |
| Not applicable | No mycological evidence available at baseline |

10.5 Safety Review

A comparison of adverse events reported per study arm will be quantified and compared.

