2.3 Potential Risks and Benefits

2.3.1 Potential Risks

All medical treatments have the potential of causing undesirable effects. For this reason, the study is performed under carefully controlled conditions.

Common side effects reported to date in patients taking conventional itraconazole (reported in 1-10% of the patients):

- Vomiting
- Diarrhea
- Abdominal pain
- Anorexia
- Edema
- Fatigue
- Fever
- Malaise
- Rash*
- Pruritus

- Headache
- Dizziness
- Libido Decreased
- Somnolence
- Hypertension
- Hypokalemia
- Albuminuria
- Hepatic Function Abnormal
- Impotence

Nausea (11%) is a common side effect (reported in more than 10% of patients) associated with other marketed azoles that may or may not be associated with SUBA-Itraconazole.

Common side effects that were reported in less than 10% of patients taking other marketed azoles (fluconazole, voriconazole, itraconazole, ketoconazole, posaconazole, isavuconazole) were:

- Dizziness
- Chest pain
- Flatulence
- Sleeplessness
- Liver function test abnormalities
- Renal insufficiency

- Trouble Breathing
- Digestion problems
- Tremors
- Asthenia (weakness)
- Cardiovascular problems such as tachycardia or arrhythmia
- Vision disturbances

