5.2 Subject Exclusion Criteria

All subjects meeting any of these listed exclusion criteria at baseline will be excluded from study participation:

- 1. Significant liver dysfunction as evidenced by at least 5 times greater than upper limits of normal baseline ALT, AST, alkaline phosphatase, or total bilirubin.
- 2. Use of an alternative antifungal therapy (IV or oral) for more than 14 days for this infection with the exception of Coccidioidomycosis. Subjects with Coccidioidomycosis who previously received fluconazole therapy for more than 14 days may be included, if in the opinion of the investigator, they are having an inadequate response or, are intolerant of fluconazole (e.g. due to adverse events). Such subjects must washout from fluconazole for 7 days (~5 half-lives of fluconazole) before starting investigational therapy.
- 3. Evidence of CNS infection.
- 4. Unable to take PO medications.
- 5. Female subjects who are lactating or pregnant.

- 6. Female subjects should be:
 - a) Postmenopausal for 1 year,
 - b) Post-hysterectomy or bilateral oophorectomy,
 - c) If of child bearing potential have a negative β-HCG at screening and using highly effective method of birth control throughout course of study or remain abstinent for duration of study.
- 7. Male subjects with female partner(s) of child-bearing potential, must agree to use a medically acceptable method of contraception during the study. If their partner is pregnant, males must agree to use a condom; if their partner is of child-bearing potential, their partner must additionally be using one of the following methods: hormonal contraception, intra-uterine device, diaphragm, or cervical cap. Spermicides alone are not an acceptable method of contraception. No sperm donations for 90 days post last dose of study therapy.
- 8. Documented intolerance, allergy or hypersensitivity to an azole.
- 9. Inability to comply with study treatment, study visits, and study procedures.
- 10. Known history of congestive cardiac failure on medical treatment, fungal endocarditis, or other causes of ventricular dysfunction that may outweigh the benefit of itraconazole.
- 11. Patients with active TB
- 12. Concurrent use of astemizole, rifampin/rifampicin, rifabutin, ergot alkaloids, long acting barbiturates, carbamazepine, pimozide, quinidine, neostigmine, terfenadine, ketoconazole, valproic acid, or St. John's wort in the 5 days prior to first administration of study drug.

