APPENDIX A: SCHEDULE OF EVENTS

| Activities | Day 1 ^g (Baseline) | Day 7 (1 wk) +/- 3 days | Day 14 (2 wks) +/- 3 days | Day 28 (4wks) +/- 7 days | Day 42 (6 wks) +/- 3 days | Day 84 (3 mos) +/- 7 days | Day 180 (6 mos) +/- 7 days |
|---|----------------------------------|----------------------------------|------------------------------------|-----------------------------------|------------------------------------|------------------------------------|-------------------------------------|
| Informed Consent | Х | | | | | | |
| Review of Inclusion/Exclusion Criteria | × | | | | | | |
| Randomization | X | | | | | | |
| Medical History | X | | | | | | |
| Clinical Assessment: vital signs, PE ^a , & radiographs ^b ; | × | Х | Х | Х | Х | Х | × |
| Participant Administered SF-12 Quality of Life Survey | Х | | | | Х | | х |
| Tolerability | Х | | | Х | Х | | Х |
| βHCG - pregnancy test ^c | Х | | | | | | |
| Mycologic Assessment: clinical, urine and serum quantitative antigen levels^d & serum antibodies ^{e,f} | х | | х | Х | Х | Х | х |
| Serum and Urine for future use: blood, urine, saliva, sputume | X | | Х | X | Х | Х | Х |
| Plasma PK ^f | | Χ | Х | | Х | | |
| Chemistry: Creatinine, AST and Alkaline Phosphatase, Total Bilirubin ^f | Х | | Х | Х | Х | Х | х |
| Hematology: CBC with Differential ^f | X | | | X | | X | X |
| HIV Status: Documentation of any positive test; Documentation of Negative test 30 days or less prior to start of study drug. | Х | | | | | | |
| Antifungal Therapy (Pre- and during study) | Х | Х | Х | Х | Х | Х | Х |
| Dose Modifications | | | Х | X | Х | Х | |
| Study Drug Dosing & Accountability | Х | Х | Х | Х | Х | Х | Х |
| Concomitant Therapy | Х | Х | Х | Х | Х | Х | Х |
| Adverse Events | Х | Х | Х | Х | Х | Х | Х |
| Days of Hospitalization, ICU | Х | Х | Х | Х | Х | Х | Х |

^a Complete physical exam on baseline; targeted physical exams for all other visits.

b Radiograph results that were performed as standard of care to diagnose or assess the fungal infection.

^C Urine or Serum pregnancy test is acceptable.

^d Histoplasma and Coccidioides urine and serum quantitative antigen.

^e Collection of sputum, if associated with the IFI and available.

^fChemistry and hematology will be processed at the site for safety evaluations; PK samples will be sent to a central lab for processing; see Manual of Procedures for specimen handling procedures;

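### Safety is compared only through adverse events recorded by unmasked clinicians; the scheduled liver chemistry and vital signs have no planned by-arm summary

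*Combined protocol and SAP*

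**What the plan says.** Section 10.3 defines Stage I safety as "adverse events that occurred in each study arm by Day 42". For Stage II it gives "Adverse events that occurred in each study arm between Days 43" up to Day 180 or end of therapy. Section 10.5 adds only that "A comparison of adverse events reported per study arm will be quantified and compared". Section 10.1 carries its t-tests, chi-square tests and regression models over to these endpoints: "The same aforementioned statistics techniques will be used for the secondary outcomes of Stage I as well as the primary and secondary outcomes of Stage" (the second stage is meant). It names no laboratory or vital-sign variable.

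The measurements themselves are planned. Appendix A has a row "Chemistry: Creatinine, AST and Alkaline Phosphatase, Total Bilirubin", marked at baseline and Days 14, 28, 42, 84 and 180. Its clinical assessment row, which includes vital signs, is marked at all seven visits. Section 14.2 has clinical laboratory data entered in the trial database. Section 2.3.1 lists "Hepatic Function Abnormal" and hypertension among side effects seen in 1-10% of patients on conventional itraconazole.

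Two provisions affect how a liver-test rise becomes an adverse event. Section 5.2 excludes "Significant liver dysfunction as evidenced by at least 5 times greater than upper limits of normal", so patients with lesser elevations can enter. Section 8.4.1 says a condition "present at the time that the patient is screened should be considered as baseline and not reported as an AE" unless it later worsens.

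**The concern.** The plan collects an objective record of liver function and blood pressure, then compares the arms only on events that passed through a clinician's decision to record them. That clinician knows the assigned capsule. Section 8.4.1 allows an abnormal laboratory result to be an adverse event but sets no size at which it becomes one. It refers to a protocol-defined grading system, but no laboratory grading table is in the document. For a patient who enters with raised liver tests, the amount of further rise that counts as worsening is also left open.

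The adverse-event count can therefore understate a hepatic difference between the formulations if rises go unrecorded. It can also distort one if recording differs by arm. A table of measured values does not depend on that step. If such tables are produced without a plan, the analyte, cut-off, time window and treatment of abnormal baselines will be chosen after unmasked data are available.

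**Working it through.** **1. Arm size.** Section 10.2 gives 80 randomized patients and 77% power, but no allocation ratio. With 40 per arm, the standard error is √(94.0²/40 + 101.8²/40) = √479.98 = 21.91 and the noncentrality is 60.0/21.91 = 2.74. The Welch t-test on 77.5 df then has power 77.2%. The stated figure is reproduced, which supports 40 per arm as the working assumption. This figure concerns the pharmacokinetic endpoint and is not in dispute.

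**2. What is collected and what is compared.**

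| Item | Follow-up visits (Appendix A) | By-arm analysis in Section 10 |
|---|---|---|
| Liver chemistry | 5 (Days 14, 28, 42, 84, 180) | none |
| Vital signs | 6 (Days 7, 14, 28, 42, 84, 180) | none |
| Adverse events | 6 | yes (10.3, 10.5) |

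At most 80 × 5 = 400 chemistry panels and 80 × 6 = 480 vital-sign sets are involved. These are ceilings, since withdrawals and missed visits will reduce them.

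**3. Unequal recording with no true difference.** Let π be the true proportion with an abnormality, the same in both arms, and r₁, r₂ the fractions recorded. Recorded counts are Binomial(40, πr₁) and Binomial(40, πr₂). The chance of a nominally significant result is the sum of Bin(a; 40, πr₁) × Bin(b; 40, πr₂) over all pairs (a, b) for which Fisher's two-sided P<0.05. The recording fractions are assumptions, as the document gives none.

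| True rate, both arms | Recording | Expected recorded per arm | P<0.05 |
|---|---|---|---|
| 5% | 80% v 40% | 1.6 v 0.8 | 0.2% |
| 5% | 90% v 30% | 1.8 v 0.6 | 0.5% |
| 10% | 80% v 40% | 3.2 v 1.6 | 2.4% |
| 10% | 90% v 30% | 3.6 v 1.2 | 5.4% |
| 20% | 80% v 40% | 6.4 v 3.2 | 11.3% |
| 20% | 90% v 30% | 7.2 v 2.4 | 25.9% |

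For reference, 50% recording in both arms at a true 20% gives 1.7%. At a true 1%, both unequal patterns give about 0%.

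**4. Incomplete but equal recording with a true difference.** Same test, 40 per arm:

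| True rates | Power, all recorded | Power, half recorded |
|---|---|---|
| 10% v 1% | 15.0% | 1.1% |
| 10% v 5% | 4.3% | 0.5% |
| 25% v 5% | 64.6% | 19.5% |

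**5. What measured values could show.** At 80% power and two-sided 0.05, a comparison of two proportions (normal approximation, 40 per arm) needs about 20% against 1%, 28% against 5%, or 36% against 10%. A comparison of a continuous value (t-test, 78 df) needs about 0.64 SD. A formal threshold test could therefore find only large differences, which points to descriptive reporting.

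**The case against.** **The reporting rules are inclusive.** Section 8.4.1 tells sites to report when unsure whether an observation is an adverse event, to document events regardless of relationship, and to record any deterioration of a baseline condition. A reader might infer that counting a liver-test rise is purely a matter of choice. The text does not support that. Some discretion remains because no size of change is defined.

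**The Data Review Committee may see the data.** Section 8.6 has it assess safety data on each arm, with data elements to be set in a charter, and Section 10.4 mentions laboratory reports. So one cannot say that nobody will look at liver tests by arm. But Section 10.4 tabulates only clinical and mycological response, Section 8.6 singles out serious suspected adverse reactions, and the charter is not in the document. This is oversight and does not specify a by-arm analysis.

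**The larger figures need rates above the document's range.** The 11.3% and 25.9% results assume a true rate of 20%, against 1-10% in Section 2.3.1. At 10% they fall to 2.4% and 5.4%, and at 5% or below they are negligible. Measured elevations may be more frequent than reported side effects, but the document gives no such rate. Nothing in it suggests that recording would differ two- or three-fold between two itraconazole capsules. This objection stands.

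**Abnormal liver function is one unranked item in the Section 2.3.1 list.** The document does not call it the main harm. It is singled out here because the schedule measures it repeatedly.

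**Conclusion.** The point holds in a limited form. Safety is defined and tested only through reported adverse events in an open-label trial, and the scheduled liver chemistry and vital signs have no by-arm use. Neither the reporting rules nor the committee wording fills that gap.

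A reader might go further and conclude that hepatic toxicity will be missed, or that a false difference is likely. The documents do not support either. The size is unknown: with equal true rates and strongly unequal recording, P<0.05 occurs in 2.4% to 5.4% of trials at a true 10%, and 11.3% to 25.9% at 20%, with 40 per arm and the recording fractions assumed. At the documented 1-10% rates, threshold comparisons have little power even with complete recording. The gain from the change is an objective description of the liver and blood-pressure data alongside the adverse-event counts, with no promise of a decisive test. It is worth making because the data are already being collected.

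**What to change.** First reconcile the liver panel. Section 8.2.1 lists ALT but not alkaline phosphatase, and Appendix A lists alkaline phosphatase but not ALT, while Section 5.2 uses both, with AST and total bilirubin, for eligibility.

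Then keep the adverse-event comparison and add to Section 10.5, by arm, to Day 42 and to Day 180:

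- the number of patients whose worst post-baseline value exceeds 3 and 5 times the upper limit of normal, for each liver test in the reconciled panel;
- for patients abnormal at entry, the worst value as a multiple of their own baseline;
- baseline-to-worst shift tables;
- change from Day 1 in blood pressure.

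Report these descriptively with confidence intervals. Use the worst on-study value as the main summary, because Section 6.3 permits dose reduction or cessation and a value at a fixed day may follow such a change. A baseline-adjusted comparison of log(value/upper limit) at Day 42 and Day 180 can be supportive only. These cut-offs are for reporting and change no clinical rule.

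The cost is recording the local upper limit of normal with each result, from about 20 sites plus any remote or commercial laboratories allowed under Section 7.3, and a few extra tables. No visit is added, and no test beyond whatever the reconciled panel settles.
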